9.8 Multiplicity

Two main objectives will be evaluated in this study. A gatekeeping procedure that controls the overall FWER associated with the primary and secondary analyses will be used. The primary hypothesis (H1) is that MOV is superior to placebo for the prevention of laboratoryconfirmed COVID-19 in participants with undetectable SARS-CoV-2 in baseline NP swabs through Day 14. As stated in Section 9.6.1, the null hypothesis $p_t \ge p_c$ will be tested versus the alternative hypothesis $p_t < p_c$. The secondary hypothesis (H2) is that MOV is superior to placebo for the prevention of laboratory-confirmed COVID-19 in participants regardless of SARS-CoV-2 results in baseline NP swabs through Day 14. As stated in Section 9.6.1, this will be evaluated by testing the null hypothesis $p_{ts} \ge p_{cs}$ versus the alternative hypothesis $p_{ts} < p_{cs}$ pcs.

MK-4482-013-05 FINAL PROTOCOL

99

As stated in Section 9.7, although there is no plan to stop the study early for efficacy, a small statistical penalty (α =0.0001) will be applied for this interim analysis using a Haybittle-Peto type adjustment [Haybittle, J. L. 1971] [Peto, R, et al 1976]. The final analysis will be conducted at a 0.0249 alpha-level to preserve the overall type I error level.

Testing begins with the primary hypothesis (H1). The secondary hypothesis (H2) will be tested only if H1 is rejected. Both tests will be performed at the same one-sided 2.49% alpha-level. If H1 fails to reach statistical significance, then H2 will not be tested. In this way, the overall one-sided 2.5% type I error rate is controlled.

9.9 Sample Size and Power Calculations

9.9.1 Sample Size and Power Calculations for Efficacy Analyses (Primary Objective)

The study will enroll approximately 1376 participants (regardless of SARS-CoV-2 results in baseline NP swabs) in a 1:1 ratio to MOV and placebo groups. Assuming approximately 80% of the 1376 participants will have undetectable SARS-CoV-2 at baseline (see Section 4.2.3), approximately 1100 participants will have undetectable SARS-CoV-2 at baseline and 276 participants will have detectable SARS-CoV-2 at baseline.

The primary endpoint of this study is the percentage of participants with undetectable SARS-CoV-2 in baseline NP swabs developing COVID-19 through Day 14. Thus, the primary analysis population consists of the approximately 1100 participants with undetectable SARS-CoV-2 at baseline, which is a subset of the 1376 participants randomized that is based on a factor (SARS-CoV-2 results in baseline NP swabs) that will not be available before randomization.

Moreover, because this factor cannot be used for stratification at randomization, the allocation of the participants with undetectable SARS-CoV-2 in baseline NP swabs randomized to the 2 intervention groups may not be in a 1:1 ratio. If at least 10% of the approximately 276 participants with detectable SARS-CoV-2 in baseline NP swabs are randomized to the MOV group, the study has at least 90% power to demonstrate the superiority of MOV over placebo for participants with undetectable SARS-CoV-2 in baseline NP swabs at an overall one-sided 2.5% alpha-level. The power and sample size calculation for the primary objective were computed using EAST and based on the following assumptions:

- The percentage of participants with undetectable SARS-CoV-2 in baseline NP swabs is assumed to be 80% among the 1376 participants (see Section 4.2.3), resulting in approximately 1100 participants with undetectable SARS-CoV-2 in baseline NP swabs.
- The background secondary attack rate, in the absence of MOV, for participants with undetectable SARS-CoV-2 in baseline NP swabs, is assumed to be ~8% [Regeneron Pharmaceuticals, Inc. 2021].

- MOV is assumed to reduce the background secondary attack rate for participants with undetectable SARS-CoV-2 in baseline NP swabs by 60%, resulting in a secondary attack rate of ~3.2% in the MOV group.
- A futility interim analysis at 55% information as outlined in Section 9.7. The Haybittle-Peto type adjustment [Haybittle, J. L. 1971] [Peto, R, et al 1976] with a small amount of alpha (α =0.0001) will be applied to this interim analysis.

Some selected power and sample size calculations are presented in Table 7, including the extreme cases where all participants with detectable SARS-CoV-2 in baseline NP swabs are either in the MOV or the placebo group, and some less-extreme scenarios:

- 1. In the scenario where the approximately 276 participants with detectable SARS-CoV-2 in baseline NP swabs are balanced between the 2 intervention groups (allocation ratio of 1), approximately 550 participants with undetectable SARS-CoV-2 in baseline NP swabs would be randomized to each group.
- 2. In the scenario where the approximately 276 participants are all randomized to the MOV group, there would be approximately 412 participants with undetectable SARS-CoV-2 in baseline NP swabs in this group versus approximately 688 in the placebo group, with an allocation ratio (MOV versus placebo) of 0.6.
- 3. In the scenario where the approximately 276 participants are all randomized to the placebo group, there would be approximately 688 participants with undetectable SARS-CoV-2 in baseline NP swabs in the MOV group versus approximately 412 in the placebo group with an allocation ratio of 1.67.
- 4. Two additional scenarios with allocation ratios of 1.5 and 0.85 are also provided.

All scenarios are based on a total sample size of 1100 participants with undetectable SARS-CoV-2 in baseline NP swabs and an overall one-sided, 2.5% alpha-level.

Table 7Power Analysis to Assess the Primary Objective in Participants WithUndetectable SARS-CoV-2 in Baseline NP Swabs; N=1100 Participants, OverallAlpha=0.025, One-sided

Sample Size	Allocation Ratio	Sample Size in MOV	Sample Size in Placebo	Power (%)
1100	1.67	688	412	89
1100	1.5	660	440	90
1100	1	550	550	93
1100	0.85	505	595	94
1100	0.6	412	688	94
MOV=molnupiravir	; NP=nasopharyngeal			

As shown in Table 7, the power in the first scenario (the extreme case where all approximately 276 participants with detectable SARS-CoV-2 in baseline NP swabs are in the placebo group) is approximately 89%. In scenarios where at least 10% of the participants with detectable SARS-CoV-2 in baseline NP swabs are in the MOV group, there is at least 90% power.

Moreover, as long as the event rate reduction is at least 54%, the study has over 80% power in the most extreme scenario (when all participants with detectable SARS-CoV-2 in baseline NP swabs, expected to be approximately 276, are in the placebo group).

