8.2.6 Assessment of Prophylaxis Outcome

The clinical outcome of prophylaxis will be assessed at the Day 14 and Day 29 visits for all participants and at the COVID-19 Confirmation Visit for participants who develop laboratory-confirmed COVID-19 with symptoms (see Section 1.3.1). Assessments should be made according to the following definitions:

Term	Definition		
Clinical Success	The participant does not develop laboratory-confirmed COVID-19 with onset within the window of interest (ie, symptom onset on or before Day 14 for the Visit 4 assessment; and on or before Day 29 for Visit 6 assessment).		
	Note: Participants who remain asymptomatic through Day 14 (or Day 29, for the Day 29 endpoint) are also considered clinical successes regardless of SARS-CoV-2 results (positive, negative, or missing).		
Clinical Failure	The participant develops laboratory-confirmed COVID-19 with onset within the window of interest (ie, symptom onset on or before Day 14 for the Visit 4 assessment; and on or before Day 29 for Visit 6 assessment).		
	The date of onset is considered the date of onset of symptoms. Note: An assessment of "Clinical Failure" on or before Day 14/Visit 4 will also be carried forward to the Day 29/Visit 6 assessment.		
Indeterminate	The outcome is indeterminate if any of the following apply:		
	• The participant is lost to follow-up during or has discontinued from the study prior to the window of interest (ie, prior to Visit 4 or Visit 6 for the outcome assessments conducted at those visits).		
	Note: This definition does not apply to participants who developed laboratory-confirmed COVID-19 with symptoms prior to leaving the study. For those participants, prophylaxis outcome should be assessed as "Clinical Failure" per the definition above.		
	• Death unrelated to COVID-19.		
	• The participant is symptomatic and missing the required viral test for confirmation of COVID-19.		
	Note: A virus-detectable NP swab collected within +/-5 days of symptom onset is considered to be within an acceptable window to confirm onset of COVID-19. A virus-undetectable NP swab that is collected within 5 days after symptom onset is considered to be within an acceptable window to rule out COVID-19.		
	NP swabs collected outside these windows are considered missing.		
	• There are other extenuating circumstances that preclude classification as a clinical success or failure, such as:		

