	 Primary efficacy hypothesis (H1) testing superiority of MOV compared with placebo in participants with undetectable SARS-CoV-2 in baseline NP swabs through Day 14
	 Secondary hypothesis (H2) testing superiority of MOV compared with placebo in participants regardless of SARS-CoV-2 results in baseline NP swabs through Day 14
	The primary hypothesis (H1) will be tested first. The secondary hypothesis (H2) will be tested only if H1 is rejected. If H1 fails to reach statistical significance, then H2 will not be tested.
	Although there is no plan to stop the study early for efficacy at the interim analysis, a small statistical penalty (α =0.0001) will be applied for this interim analysis. The final analysis will be conducted at 0.0249 alpha-level to preserve the type I error level.
Sample Size and Power	The study will enroll approximately 1376 participants (regardless of SARS-CoV-2 results in baseline NP swabs; approximately 688 each in MOV 800 mg and in the placebo group). Assuming approximately 20% of the 1376 participants will have detectable SARS-CoV-2 at baseline [O'Brien, M. P., et al 2021], this will result in approximately 1100 participants with undetectable SARS-CoV-2 at baseline.
	The primary objective will be assessed on the approximately 1100 participants with undetectable SARS-CoV-2 in baseline NP swabs.
	Assume:
	• A background secondary attack rate of 8% and an underlying treatment difference (MOV minus placebo) in percentage of participants developing COVID-19 through Day 14 of -4.8 percentage points (a 60% relative reduction in attack rate).
	• At least 10% of the approximately 276 participants with detectable SARS-CoV-2 in baseline NP swabs are randomized to the MOV group.

The study has at least 90% power to demonstrate that MOV is
superior to placebo for prevention of confirmed COVID-19 in
household contacts (with undetectable SARS-CoV-2 in baseline
NP swabs) of an index case through Day 14 at an overall
one-sided 2.5% alpha-level.
Details are provided in Section 9.9.1.

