9.6.1 Statistical Methods for Efficacy Analyses

For the evaluation of the primary hypothesis, the superiority of MOV compared with placebo with respect to the percentage of participants with undetectable SARS-CoV-2 in baseline NP swabs developing COVID-19 by Day 14 will be assessed using the stratified Miettinen and Nurminen method with CMH weights [Miettinen, O. and Nurminen, M. 1985]. Stratification factors include age and household size as specified in Section 6.3.2. The primary hypothesis will be addressed by testing the null hypothesis $p_t \ge p_c$ versus the alternative hypothesis $p_t < p_c$, where p_t and p_c refer to event rates in MOV and placebo groups in participants with undetectable SARS-CoV-2 in baseline NP swabs, respectively. The null hypothesis will be rejected if the 1-sided p-value is less than 0.0249 (see Section 9.8 for alpha adjustment) and the superiority of MOV relative to placebo will be demonstrated for the primary endpoint.

For the analysis of this primary endpoint in the mITT-VN population, the following Table shows how to handle the indeterminate clinical outcomes of prophylaxis presented in Section 8.2.6 (Table 4).

Indeterminate Prophylaxis Outcomes	Imputation	
Lost to follow-up during or discontinued from the study prior to the window of interest (ie, prior to Visit 4 or Visit 6 for the outcome assessments conducted at those visits). This does not include participants who were already determined to be clinical failures prior to being lost to follow-up or discontinued.	Considered a case of COVID-19	
Death unrelated to COVID-19	Considered a case of COVID-19	
Missing the required viral test for confirmation of COVID-19 (see also Section 8.2.6 for details around acceptable windows)	Considered a case of COVID-19	
Other extenuating circumstances that preclude classification as a clinical success or failure (such as the participant receives another agent for the prevention of COVID-19)	Considered a case of COVID-19	
Participants in Ukraine who were randomized in FEB-2022 without clinical outcome assessment on Day 14 will be excluded from the efficacy analysis.		

Table 4 Imputation for Indeterminate Prophylaxis Outcomes

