Moreover, a participant without a Day 14 clinical outcome assessment, but assessed as a clinical success through Day 29 will be treated as a clinical success through Day 14. A participant without a Day 29 clinical outcome assessment, but assessed as a clinical failure through Day 14 will be treated as a clinical failure through Day 29. If a participant discontinued from the study prior to the Day 14 or the Day 29 visit, but was assessed as a clinical failure from the COVID-19 Confirmation Visit, then the clinical failure should be carried forward to the Day 14 and/or the Day 29 visit after the COVID-19 Confirmation Visit. All other missing clinical outcome assessments will be imputed as clinical failures.

For the evaluation of the secondary hypothesis, the superiority of MOV compared with placebo with respect to the percentage of participants (regardless of SARS-CoV-2 results in baseline NP swabs) developing COVID-19 by Day 14 will be assessed using the same method in the primary hypothesis, ie, the stratified Miettinen and Nurminen method with CMH weights [Miettinen, O. and Nurminen, M. 1985] (stratified by age and household size as described in Section 6.3.2, and SARS-CoV-2 status in baseline NP swab). The secondary hypothesis will be evaluated by testing the null hypothesis $p_{ts} \ge p_{cs}$ versus the alternative hypothesis $p_{ts} < p_{cs}$, where p_{ts} and p_{cs} refer to event rates (percentages of participants developing COVID-19 by Day 14) in MOV and placebo groups, respectively. The null hypothesis will be rejected if the 1-sided p-value is less than 0.0249 (see Section 9.8 for alpha adjustment) and the superiority of MOV relative to placebo will be concluded for this secondary endpoint.

The efficacy of MOV compared with placebo for the prevention of COVID-19 with respect to the percentage of participants with undetectable SARS-CoV-2 in baseline NP swabs developing COVID-19 through Day 29 will be evaluated. The difference in percentages between treatment groups (MOV minus placebo) and the associated 95% CI will be

MK-4482-013-05 FINAL PROTOCOL

16-OCT-2022

calculated using the stratified Miettinen and Nurminen method with CMH weights [Miettinen, O. and Nurminen, M. 1985] (stratified by age and household size as described in Section 6.3.2).

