The allocation of the approximately 1100 participants with undetectable SARS-CoV-2 in baseline NP swabs randomized to the 2 intervention groups may not be in a 1:1 ratio, since SARS-CoV-2 in baseline NP swabs will not be available before randomization so that the number of participants in each group may vary. As an example, the case when approximately 660 participants with undetectable SARS-CoV-2 in baseline NP swabs and approximately 440 participants with undetectable SARS-CoV-2 in baseline NP swabs are randomized to MOV and placebo groups, respectively, will be discussed in this section.

The Gamma family spending function with $\gamma = -4$ will be used to set the futility boundary for the primary endpoint as a guide for the eDMC to control overall type I error rate of 0.025, one-sided. Assuming the information fraction of 55%, the nonbinding futility boundary expressed on the risk difference (MOV minus placebo) is -0.0049. The boundary crossing probabilities for futility are 59.8% under H0 and 1.4% under H1 (risk difference of -0.048). Power assessments for additional scenarios where the number of participants with undetectable SARS-CoV-2 in baseline NP swabs may be different from the scenario described above are presented in Section 9.9.1.

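### The claim of at least 90% power allows for no indeterminate outcomes, although the primary analysis counts most of them as COVID-19 cases; at an equal 2% rate power is about 84%, at 5% about 70%

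*Combined protocol and SAP*

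**What the plan says.** The power claim appears three times: in the Section 9.1 summary ("The study has at least 90% power to demonstrate that MOV is"), in the body of Section 9.9.1 ("the study has at least 90% power to demonstrate the superiority of MOV over placebo"), and under Table 7 ("are in the MOV group, there is at least 90% power"). Section 9.9.1 lists the assumptions behind it: 80% of 1376 participants virus-negative at baseline, a placebo attack rate of about 8%, a 60% reduction to about 3.2% on MOV, and a futility look at 55% information. No rate of dropout, missing or indeterminate outcome is listed, and all 1100 participants are used. Section 9.7 adds, for the 660:440 example, a nonbinding futility boundary of -0.0049 on the risk difference: "The boundary crossing probabilities for futility are 59.8% under H0 and 1.4% under H1".

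The primary mITT-VN analysis treats indeterminate outcomes as follows. Table 4 in Section 9.6.1 has four categories: loss to follow-up or discontinuation before the visit, death unrelated to COVID-19, a missing confirmatory test, and other extenuating circumstances. Each is "Considered a case of COVID-19". The text below Table 4 adds: "All other missing clinical outcome assessments will be imputed as clinical failures".

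There are exceptions:
- Section 8.2.6: "Participants who remain asymptomatic through Day 14 (or Day 29, for the Day 29 endpoint) are also considered clinical successes", even when the swab is missing.
- Section 9.6.1: a participant with no Day 14 assessment but "assessed as a clinical success through Day 29 will be treated as a clinical success through Day 14".
- Sections 9.5.1 and 9.6.1: participants in Ukraine randomized in February 2022 without a Day 14 assessment are excluded, not imputed.

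**The concern.** The imputed cases enter the event rates that are tested but not the rates that were powered. If the same share of each arm is turned into cases regardless of true outcome, the difference between arms shrinks, both rates move up to where the binomial variance is larger, and power falls on both counts.

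The plan itself creates routes to an indeterminate outcome. Any one of 15 symptoms can trigger a confirmation visit, and the 3-day window for that visit may be exceeded. An undetectable swab rules out COVID-19 only if taken within 5 days after symptom onset; a swab outside the window counts as missing, which makes a symptomatic participant a case. Withdrawals are not replaced (Section 5.5).

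A null primary result would be read against a design said to have at least 90% power. The secondary hypothesis is also tested only if the primary one succeeds, and the eDMC receives a futility probability calculated without indeterminate outcomes.

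**Working it through.** **Inputs.** From Sections 9.6.1, 9.7 and 9.9.1: one-sided alpha 0.0249 at the final analysis (z = 1.962), placebo rate 0.08, MOV rate 0.032, 1100 participants, futility stop if the interim risk difference is at or above -0.0049 at 55% information. The indeterminate share m is not in the documents; 0 to 5% is assumed.

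**Step 1: reproduce Table 7.** Unpooled normal approximation with the futility look and m = 0:

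| MOV : placebo | Reproduced (%) | Table 7 (%) |
|---|---|---|
| 688:412 | 89.1 | 89 |
| 660:440 | 90.3 | 90 |
| 550:550 | 93.3 | 93 |
| 505:595 | 93.9 | 94 |
| 412:688 | 94.2 | 94 |

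At 660:440 the H1 futility probability comes to 1.45%, against the stated 1.4%. The published figures therefore correspond to zero indeterminate outcomes.

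**Step 2: apply the imputation.** With a share m in each arm, independent of the true outcome and counted as cases, a true rate p becomes p' = p(1 - m) + m. Before the futility look, power at n = 550 per arm is Φ(difference / SE - 1.962), with SE = √{[p'c(1 - p'c) + p't(1 - p't)] / 550}.

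- m = 0: 0.0800 vs 0.0320; difference 0.0480, SE 0.01379, ratio 3.48; power 93.6%.
- m = 2%: 0.0984 vs 0.0514; difference 0.0470, SE 0.01581, ratio 2.98; power 84.5%.
- m = 5%: 0.1260 vs 0.0804; difference 0.0456, SE 0.01829, ratio 2.49; power 70.2%.

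**Step 3: use the planned type of test.** Miettinen-Nurminen score test, exact binomial enumeration, with the futility look. It is unstratified because the stratum mix is not given.

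| Equal m | 550:550, score test (%) | 550:550, Table 7 method (%) | 660:440, score test (%) |
|---|---|---|---|
| 0 | 94.0 | 93.3 | 93.4 |
| 1% | 89.5 | 88.9 | 88.8 |
| 2% | 84.4 | 84.1 | 83.7 |
| 3% | 79.4 | 79.2 | 78.6 |
| 5% | 70.1 | 69.8 | 68.9 |

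At 550:550 the score test reaches 90% at m = 0.89% (0.0089 × 1100 ≈ 10 participants) and 80% at m = 2.87% (≈ 32 participants). At 660:440 the 90% crossing is 0.75% (≈ 8 participants).

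**Step 4: allocation.** With 276 virus-positive among 1376 and 688 randomized to MOV, the hypergeometric 99.9% range is 114 to 162 virus-positive on MOV, that is virus-negative splits from 574:526 to 526:574. Across that range power is 84.2 to 84.6% at m = 2% and 69.7 to 70.1% at 5%. The 660:440 split, with 28 or fewer virus-positive on MOV, has probability about 4 × 10⁻⁵⁵.

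**Step 5: unequal rates at 550:550, score test.** 1% MOV and 2% placebo: 96.2%; reversed: 68.8%. 2% MOV and 3% placebo: 93.5%; reversed: 62.4%.

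**Step 6: H1 futility probability.** At equal m of 0, 1, 2 and 5%: 1.4, 2.2, 3.0 and 5.6% at 660:440 by the Table 7 method; 0.9, 1.6, 2.3 and 4.9% at 550:550.

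**The case against.** Table 7 contains no arithmetic error, and the power is expressly conditional on listed assumptions. The 2% and 5% rates are not the plan's. At 1% the shortfall from 90% is only half a point, and several rules hold the rate down: a failure found at a confirmation visit is carried forward after dropout, home or alternate-site visits are allowed, local-laboratory and OP results serve as fallbacks, and follow-up continues after study drug is stopped.

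The equal-rate model may also be pessimistic. A missing confirmatory test matters only in symptomatic participants, who under H1 are commoner on placebo and include true cases. By the Table 7 method, 2.0% on MOV against 2.65% on placebo keeps power at 90.6%; if half of a 2% share are untested true cases, power is 89%. The supportive Per-Protocol analysis excludes indeterminate outcomes and would be read alongside a null result; dropping 5% of participants leaves power near 92%, before its other exclusions.

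Much of this stands as a limit on size: the loss depends on a rate nobody has stated, and its direction depends on the balance between arms. It does not rescue the claim. The Per-Protocol analysis is not the primary test. The 8% is described as a background attack rate without MOV and is reduced by 60%; if it already contained imputed cases, MOV would be assumed to prevent 60% of losses to follow-up too. The choice of test matters little at 550:550 but more at 660:440, where the Table 7 method crosses 90% at m = 0.07% and gives 80.5% at 2% and 66.4% at 5%, below the score test.

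**Conclusion.** The concern holds. The figure of at least 90% is correct for its listed inputs, but it is not the power of the planned primary analysis unless indeterminate outcomes are close to zero or favour MOV. With equal rates independent of outcome and near-balanced allocation, power is about 84% at 2% and about 70% at 5%; a material loss needs roughly 2% or more. The arithmetic is firm. The rates are assumptions, and the calculation is unstratified. The effect on the futility probability is small and concerns a nonbinding boundary. This should be fixed, but it does not undermine the design.

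**What to change.** In Section 9.9.1, state the assumed indeterminate rate for each arm, with its basis, and name the test used for the power calculation. Restate Table 7, the power statements in Sections 9.1 and 9.9.1, and the H1 futility probability in Section 9.7 with the Table 4 imputation applied. Add a short sensitivity table covering equal and unequal rates; at 550:550 with the score test, equal 1%, 2% and 5% give 89%, 84% and 70%, and 1% on MOV with 2% on placebo gives 96%, or 69% reversed.

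The cost is SAP wording and one table. The stated power becomes conditional on the assumed rate and, at equal rates, less favourable. Neither the sample size nor the primary imputation rule needs to change, and no extra participants are required.

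### Table 7 gives the primary power under an unpooled normal approximation, not under the planned Miettinen-Nurminen test; two rows are 3 to 4 points too low, one is about 2 points too high, and the text implies the wrong least favourable split

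*Combined protocol and SAP*

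**What the plan says.** Section 9.6.1 states that the primary comparison "will be assessed using the stratified Miettinen and Nurminen method with CMH weights", stratified by age and household size, and that "The null hypothesis will be rejected if the 1-sided p-value is less than 0.0249".

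Section 9.9.1 describes the power work only by its software and inputs: "The power and sample size calculation for the primary objective were computed using EAST and based on the following assumptions". No test statistic or variance option is named. For virus-undetectable participants the background attack rate "is assumed to be ~8" percent, and MOV is assumed to cut this by 60%, "resulting in a secondary attack rate of ~3.2% in the MOV group".

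Table 7 then gives 89, 90, 93, 94 and 94% for MOV-to-placebo ratios of 1.67, 1.5, 1, 0.85 and 0.6. Three statements rest on it:

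- The split of 688 MOV to 412 placebo is presented as the low-power case: power when all detectable participants "in baseline NP swabs are in the placebo group) is approximately 89" percent.
- The 90% power claim carries an assumption, repeated in Section 9.1: "At least 10% of the approximately 276 participants with detectable SARS-CoV-2 in baseline NP swabs are randomized to the MOV group".
- For a smaller effect, "as long as the event rate reduction is at least 54%, the study has over 80% power in the most extreme scenario", meaning the same 688:412 split.

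**The concern.** A power table should describe the test that decides the trial. With equal arms the choice between pooled and unpooled variance hardly matters. With unequal arms and rates of 8% and 3.2% it does, and it works in opposite directions at the two ends of Table 7. The unpooled variance penalises a small placebo arm, because placebo has the higher event rate and so the larger variance. The pooled null variance penalises a large placebo arm, because it raises the pooled rate.

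If Table 7 used one method and the analysis uses the other, the printed order of the allocations misleads. A reader would learn that losing placebo participants from the primary population is the threat to power, and that losing MOV participants costs nothing.

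**Working it through.** **Inputs.** From 9.9.1: p_c = 0.08, p_t = 0.032, difference d = 0.048, N = 1100 and the five splits. From 9.6.1 and 9.8: final one-sided alpha 0.0249, so z = 1.962. From 9.7: a look at 55% information, nonbinding futility boundary of -0.0049 on the risk difference, interim alpha 0.0001.

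**Step 1: reproduce Table 7.** Unpooled approximation:

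power = Φ(d/SE1 − z), with SE1 = √[p_t(1−p_t)/n_MOV + p_c(1−p_c)/n_pbo].

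- At 688:412, SE1 = 0.01496, so Φ(0.048/0.01496 − 1.962) = Φ(1.248) = 89.4%.
- At 412:688, SE1 = 0.01350, so Φ(1.595) = 94.5%.
- Adding the futility look by numerical integration gives 89.1, 90.3, 93.3, 93.9 and 94.2%, which round to all five printed values.
- Section 9.7 gives a second check. For 660:440 it states a futility-crossing probability of 59.8% under the null. The unpooled calculation gives 59.8%; the pooled one gives 60.6%.

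**Step 2: pooled null variance.** For a null difference of zero, the Miettinen-Nurminen variance is the pooled one (apart from a factor N/(N−1)):

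power = Φ((d − z·SE0)/SE1), with SE0 = √[p̄(1−p̄)(1/n_MOV + 1/n_pbo)].

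- At 688:412, p̄ = 0.0500 and SE0 = 0.01357, giving Φ(1.429) = 92.4% (92.35% before rounding).
- At 412:688, p̄ = 0.0620 and SE0 = 0.01503, giving Φ(1.373) = 91.5%.

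The extremes change order, and the 1.67, 1.5 and 0.6 rows no longer match the table.

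**Step 3: the planned test itself.** Unstratified Miettinen-Nurminen, binomial data, 1,000,000 simulated trials per row with the futility stop; fixed-design values by exact enumeration.

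| Split MOV:placebo (ratio) | Table 7 | Unpooled approx., with look | M&N, fixed, exact | M&N, with look | Table 7 minus M&N with look |
|---|---|---|---|---|---|
| 688:412 (1.67) | 89 | 89.1 | 93.4 | 92.9 | −3.9 |
| 660:440 (1.5) | 90 | 90.3 | 93.8 | 93.4 | −3.4 |
| 550:550 (1) | 93 | 93.3 | 94.3 | 94.0 | −1.0 |
| 505:595 (0.85) | 94 | 93.9 | 93.9 | 93.7 | +0.3 |
| 412:688 (0.6) | 94 | 94.2 | 92.3 | 92.1 | +1.9 |

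The documents give no stratum shares or stratum rates. With four assumed strata and equal rates across them, a simulated stratified test (fixed design) gives 93.4, 93.8, 94.2, 93.9 and 92.2%, so stratification does not change the picture under that assumption.

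**Step 4: where the gap comes from (fixed design).** At 1.67 the unpooled formula gives 89.4%, the exact power of the Wald test is 91.6%, and that of Miettinen-Nurminen is 93.4%. About 2.2 points are normal-approximation error and about 1.7 (before rounding) are choice of test. At 1.5 the sequence is 90.6, 92.6 and 93.8%.

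**Step 5: the 54% statement.** With Miettinen-Nurminen and the futility stop, simulated power at a 54% reduction is 85.5% for 688:412 and 83.7% for 412:688. Power reaches 80% at about 51% (80.4%) and 52% (80.2%) respectively.

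**Step 6: which splits can occur.** Treating the 276 detectable participants as a random draw from 1376 split 688:688, the number on MOV has mean 138 and SD √(276 × 0.25 × 1100/1375) = 7.43. The 10% condition (28 on MOV) lies (138 − 28)/7.43 = 14.8 SD from the mean; the two extremes lie 138/7.43 = 18.6 SD away. A range of about 3 SD corresponds to 528 to 572 undetectable participants on MOV, where simulated power is about 94%.

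**The case against.** The defence has four good points, and each limits what can be said.

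- **Not an arithmetic slip.** All five rows follow from the plan's inputs under a standard variance option. The defect is a mismatch between power method and analysis method, with the power method unstated.
- **Best and worst are not swapped.** A reader might infer this because the two extremes change order. It does not follow: under the planned test 1:1 is best and 1.67 is second worst. Only the 0.6 row moves from joint best to worst.
- **The 54% and 10% statements are not false.** A reader might infer that they are, since they rest on the affected row. Both are worded as sufficient conditions, and both remain true under Miettinen-Nurminen. They are conservative: 51 to 52% already gives 80% power, and every listed split exceeds 90% without the 10% condition.
- **The trial is not underpowered.** The larger discrepancies are understatements, and the one real overstatement is at a split about 18.6 SD from expectation. Section 9.9.1 itself labels the outer rows extreme.

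The objection does not rescue the table as a description of the planned test. Even the exact Wald test, which is not planned, has 91.6% power at 688:412 in a fixed design, and 91.3% when simulated with the look, so 89% is not the power of either test. The text still presents the wrong split as the low-power case.

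**Conclusion.** The point holds as a minor reporting correction. For the test in 9.6.1, power is about 93, 93, 94, 94 and 92% across the five rows. Table 7 understates the 1.67 and 1.5 rows by about 3 to 4 points and overstates the 0.6 row by about 2. The least favourable listed split is 412 MOV to 688 placebo, and the most favourable is 1:1.

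This rests on the plan's own rates and N, on an unstratified test, and on the futility boundary being followed although it is nonbinding. That EAST was run with an unpooled variance is inferred from the match in all five rows and in the 9.7 futility probability; the documents do not say so. N, alpha, the decision rules and the claim of at least 90% power are unaffected.

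**What to change.** 1. Recompute Table 7 for the Miettinen-Nurminen test with the 55% futility look, and state the test and variance option used. If stratified power is reported, state the assumed stratum shares and rates.
2. Restate primary power as about 92 to 94% across all listed splits.
3. In 9.9.1, replace the text that makes all detectable participants on placebo the low-power case; name 412:688 as the least favourable listed split.
4. Drop the 10% condition from 9.1 and 9.9.1, since the recomputed table does not need it. The 54% sentence may stay as a conservative statement, or be replaced by the recomputed value of about 51 to 52%.

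The cost is one re-run of the power table and a text edit. The printed figure at ratio 0.6 falls from 94% to about 92%, and the figure at 1.67 rises from 89% to about 93%.
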